## 6.6. Dose Modification

Dose modifications of JNJ-3989 and NA (increase or decrease of dose level) are not permitted during the study.

For PegIFN- $\alpha$ 2a, dose adjustment guidelines are applicable for participants who develop laboratory abnormalities during PegIFN- $\alpha$ 2a treatment, as recommended in the locally approved prescribing information for PegIFN- $\alpha$ 2a and upon investigator's assessment.

Refer to the example from the Pegasys USPI and SmPC (see [Table 5](#)).

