**Table 5: PegIFN- $\alpha$ 2a Hematological Dose Modification Guidelines**

Laboratory Values	Recommended Dose
ANC <750 cells/mm 	Reduce to 135 $\mu$ g
ANC <500 cells/mm 	Discontinue treatment until ANC values return to more than 1,000 cells/mm  . Reinstitute at 90 $\mu$ g and monitor ANC.
Platelet <50,000 cells/mm 	Reduce to 90 $\mu$ g
Platelet <25,000 cells/mm 	Discontinue treatment

ANC: absolute neutrophil count

Source: Pegasys USPI and SmPC

For participants who prematurely discontinue PegIFN- $\alpha$ 2a, treatment with PegIFN- $\alpha$ 2a may be restarted according to the recommendations from the locally approved prescribing information for PegIFN- $\alpha$ 2a.

### 6.6.1. Study Intervention Completion at Week 48

With the implementation of Protocol Amendment 5, all participants had to stop JNJ-6379 treatment immediately.

Participants will complete treatment with JNJ-3989 after a fixed duration of 48 weeks. If all of the below criteria are met based on clinical laboratory tests performed at Week 44, treatment with NA will also be completed at the next scheduled visit (ie, Week 48):

- The participant has ALT <3x ULN, AND
- The participant has HBV DNA <LLOQ, AND
- The participant is HBeAg negative, AND
- The participant has HBsAg <10 IU/mL.

**Note:** In case of ALT elevation  $\geq 3$ x ULN at Week 44 the investigator must consider different potential causes of increased ALT to ensure appropriate work up and management as needed. If the ALT elevation is unrelated to HBV activity and/or <3x ULN by Week 48, NA completion may be considered at the discretion of the investigator and in consultation with the sponsor.

Participants who do not meet the above criteria at Week 48 should continue NA treatment during the 48-week follow-up phase. Participants who are receiving optional treatment with PegIFN- $\alpha$ 2a and who have not met NA treatment completion criteria at Week 48 may have NA treatment completion criteria assessed at the end of treatment with PegIFN- $\alpha$ 2a and stop NA if criteria are met.

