## 7. DISCONTINUATION OF INVESTIGATIONAL INTERVENTION AND PARTICIPANT DISCONTINUATION/WITHDRAWAL

### 7.1. Discontinuation of Study Intervention

With the implementation of Protocol Amendment 5, all participants had to stop JNJ-6379 treatment immediately.

Treatment with JNJ-3989 and/or PegIFN- $\alpha$ 2a must be discontinued if any of the criteria listed below apply. If JNJ-3989 is discontinued, PegIFN- $\alpha$ 2a should also be discontinued. If PegIFN- $\alpha$ 2a is discontinued, JNJ-3989 should be continued. NA treatment may be continued or, in consultation with the sponsor or discontinued based on investigator judgement.

- The participant withdraws consent to receive study intervention.
- The investigator believes that for safety reasons or tolerability reasons (eg, AE) it is in the best interest of the participant to discontinue JNJ-3989 (and, if applicable, PegIFN- $\alpha$ 2a).
- The participant becomes pregnant.
- The participant has a  $\geq$ grade 3 rash (see Section 10.5, Appendix 5, Rash Management) or allergic reaction (see Section 8.5.7.2).
- The participant has signs of hepatic decompensation (ie, clinical evidence of ascites, bleeding varices, or hepatic encephalopathy) or an increase in direct bilirubin  $>1.5$ x ULN in combination with INR  $\geq 1.5$ x ULN or albumin  $<3.0$  g/dL.
- The participant has a confirmed  $\geq$ grade 3 eGFRcr abnormality and a drop from baseline of  $>10$  mL/min/1.73 m^2, considered at least possibly related to JNJ-3989 (or PegIFN- $\alpha$ 2a) that persists despite changing tenofovir disoproxil to ETV or TAF (if the patient was receiving tenofovir disoproxil) (see Section 8.5.6.4).
- The participant has a confirmed QTcF prolongation (defined as a QTcF value of  $>500$  ms, or an increase from baseline of  $>60$  ms) at any given time point.
- The participant requires  $\geq 7$  days of treatment with any of the disallowed medications listed in Section 6.5 and does not intend to discontinue treatment with the disallowed medication.

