- The participant has confirmed HBV virologic breakthrough (ie, confirmed on-treatment HBV DNA increase by  $>1 \log_{10}$  IU/mL from nadir or confirmed on-treatment HBV DNA level  $>200$  IU/mL in participants who had HBV DNA level  $<\text{LLOQ}$  of the HBV DNA assay). In case of virologic breakthrough, the same assessments will be done at an unscheduled visit as will be done in case of an ALT flare, but no PBMC sample will be taken (see Section 8.5.6.1 and Schedule of Activities), changing the NA should be considered in consultation with the sponsor.

If virologic breakthrough occurs during JNJ-3989 and PegIFN- $\alpha$ 2a administration, this does not automatically lead to stop of JNJ-3989 and/or PegIFN- $\alpha$ 2a but should be assessed/discussed with the Sponsor.

In case of virologic breakthrough, a viral sequencing sample will be collected at the next visit.

- The participant has ALT/AST elevations, as described in Section 8.5.6.2.
- The participant has confirmed  $\geq$ grade 3 hematologic abnormalities as described in Section 8.5.6.5.

**NOTE:** The grades are based on the DAIDS Toxicity Grading Scale (see Section 10.9, Appendix 9, DAIDS Table).

In addition, PegIFN- $\alpha$ 2a (if applicable) must immediately be discontinued for any of the following reasons:

- Participant has platelet count  $<25,000$  cells/mm $^3$
- Participant has ANC  $<500$  cells/mm $^3$

**Note:** PegIFN- $\alpha$ 2a treatment can be restarted when ANC values return to more than 1,000 cells/mm $^3$  (see details in Section 6.6, Dose Modification)

- Participant develops evidence of hepatic decompensation during treatment, or ALT increase clinically significant or accompanied by direct bilirubin increase
- Participant develops thyroid disorders or diabetes during treatment and cannot be controlled with medication
- Participant develops new or worsening ophthalmologic disorders
- Participant develops any deterioration of cardiovascular status
- Participant develops serious, acute hypersensitivity reaction (eg, urticaria, angioedema, bronchoconstriction, anaphylaxis)
- Participant develops serious infection (bacterial, viral, fungal) and/or sepsis
- Participant develops persistent or unexplained pulmonary infiltrates or pulmonary function impairment
- Participant with onset or worsening of psoriatic lesion
- Participant develops moderate or severe depression, or other psychiatric symptoms (for mild depression, treatment discontinuation may be considered)

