### **8.5.6.5. Hematologic Abnormalities**

Mild thrombocytopenia was observed in recently conducted non-clinical toxicology studies with the combination of JNJ-3989 and JNJ-6379. In addition, in a 3-month combination study with 80 rats, 1 rat developed pancytopenia related to bone marrow depletion after 23 days of dosing. Previously, in a 9-month dog study in 24 dogs treated with JNJ-6379 alone, pancytopenia which correlated with a marked increase in plasma cell-like cells in the bone marrow was observed in 1 dog after 60 days of dosing.

No thrombocytopenia or pancytopenia has been observed in the ongoing JADE study (56136379HPB2001) investigating JNJ-6379/Placebo with or without NA treatment. All 232 participants have completed at least 24 weeks of study intervention. In a Phase 1 study with JNJ-3989, mild (Grade 1) transient thrombocytopenia was observed in 6 out of 84 participants receiving 3 SC injections of JNJ-3989 alone over a period of up to 12 weeks with background of NA. The transient thrombocytopenia was not considered clinically significant. No thrombocytopenia or pancytopenia was observed in 12 participants when JNJ-3989 and JNJ-6379 were given in combination over a 12-week period.

Based on the non-clinical findings, any relevant abnormalities in hematologic parameters will be carefully monitored as described below:

- Platelet counts: <100, 000 cells/mm^3 (at least Grade 2 [DAIDS]) or <100 GI/L or reduction from baseline by at least 50% baseline
- Hemoglobin: Decrease from baseline of at least 2 g/dL from baseline or at least Grade 2 (DAIDS)
- Reticulocyte count: Reduction to <0.5% of the RBC count
- Neutrophil count: Treatment-emergent reduction to at least Grade 2 (DAIDS)

In case any one of the above criteria are met, a confirmatory visit should be scheduled as soon as possible, preferably within 7 days of the receipt of the initial results. Confirmation of the results will trigger weekly or biweekly (every other week) unscheduled visits until improvement or stabilization of the respective parameter(s). Stabilization is defined as no further significant reduction over two consecutive visits.

In case of confirmed Grade 3 or Grade 4 hematologic abnormalities, discontinuation of JNJ-3989 (and PegIFN- $\alpha$ 2a, if applicable) should be considered. In case of discontinuation, NA treatment should be continued.

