aged 22 to 35 days (male and female)	9.5 to 11.0 5.88 to 6.86	8.0 to <9.5 4.94 to <5.88	6.7 to <8.0 4.15 to <4.94	<6.7 $<4.15$
aged 8 to ≤21 days (male and female)	11.0 to 13.0 6.81 to 8.10	9.0 to <11.0 5.57 to <6.81	8.0 to <9.0 4.96 to <5.57	<8.0 $<4.96$
aged ≤7 days (male and female)	13.0 to 14.0 8.05 to 8.72	10.0 to <13.0 6.19 to <8.05	9.0 to <10.0 5.59 to <6.19	<9.0 $<5.59$

HIV: human immunodeficiency virus; LLN: lower limit of normal

s Revised by the sponsor.

t Male and female sex are defined as sex at birth. For transgender participants aged ≥13 years who have been on hormone therapy for more than 6 consecutive months, grade hemoglobin based on the gender with which they identify (ie, a transgender female should be graded using the female sex at birth hemoglobin laboratory values).

u The most commonly used conversion factor to convert g/dL to mmol/L is 0.6206. For grading hemoglobin results obtained by an analytic method with a conversion factor other than 0.6206, the result must be converted to g/dL using the appropriate conversion factor for the particular laboratory.

LABORATORY VALUES				
HEMATOLOGY				
PARAMETER	GRADE 1 MILD	GRADE 2 MODERATE	GRADE 3 SEVERE	GRADE 4 POTENTIALLY LIFE- THREATENING
INR, High (not on anticoagulation therapy)	1.1 to $<1.5 \times \text{ULN}$	1.5 to $<2.0 \times \text{ULN}$	2.0 to $<3.0 \times \text{ULN}$	$\geq 3.0 \times \text{ULN}$
Methemoglobin (% hemoglobin)	5.0% to $<10.0\%$	10.0% to $<15.0\%$	15.0% to $<20.0\%$	$\geq 20.0\%$
PTT, High (not on anticoagulation therapy)	1.1 to $<1.66 \times \text{ULN}$	1.66 to $<2.33 \times \text{ULN}$	2.33 to $<3.00 \times \text{ULN}$	$\geq 3.00 \times \text{ULN}$
Platelets, Decreased (cells/mm  ; cells/L)	100,000 to $<125,000$ $100.000 \times 10^9$ to $<125.000 \times 10^9$	50,000 to $<100,000$ $50.000 \times 10^9$ to $<100.000 \times 10^9$	25,000 to $<50,000$ $25.000 \times 10^9$ to $<50.000 \times 10^9$	$<25,000$ $<25.000 \times 10^9$
PT, High (not on anticoagulation therapy)	1.1 to $<1.25 \times \text{ULN}$	1.25 to $<1.50 \times \text{ULN}$	1.50 to $<3.00 \times \text{ULN}$	$\geq 3.00 \times \text{ULN}$
WBC, Decreased (cells/mm  ; cells/L) aged > 7 days	2,000 to 2,499 $2.000 \times 10^9$ to $2.499 \times 10^9$	1,500 to 1,999 $1.500 \times 10^9$ to $1.999 \times 10^9$	1,000 to 1,499 $1.000 \times 10^9$ to $1.499 \times 10^9$	$<1,000$ $<1.000 \times 10^9$

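### Protocol 7.1 makes a confirmed grade 3 or higher hematologic abnormality a mandatory stop, but 8.5.6.5 only asks that stopping be considered; for optional PegIFN-α2a, Table 5 adds dose reduction at some grade 3 values

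*Protocol*

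**What the plan says.** Section 7.1 of the Protocol opens its general stopping list by stating that treatment with JNJ-3989 and/or PegIFN-α2a "must be discontinued if any of the criteria listed below apply". One criterion on that list is confirmed abnormalities of at least "grade 3 hematologic abnormalities as described in Section 8.5.6.5". Grades are DAIDS grades (Appendix 9).

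Section 8.5.6.5 covers the same finding: "In case of confirmed Grade 3 or Grade 4 hematologic abnormalities, discontinuation of JNJ-3989", and of PegIFN-α2a where it is used, is the action named. The sentence ends "2a, if applicable) should be considered".

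Section 6.6 does not permit dose changes for JNJ-3989 or the NA. For PegIFN-α2a it allows adjustment according to the local prescribing information and the investigator's assessment, and introduces Table 5 with "Refer to the example from the Pegasys USPI and SmPC". In that table the row "Platelet <50,000 cells/mm"³ leads to a reduced dose, as does ANC below 750. Stopping appears at platelets below 25,000 and ANC below 500.

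A second list in 7.1, for PegIFN-α2a alone, calls for an immediate stop at those same two lower limits and allows restart once ANC exceeds 1,000.

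**The concern.** A stopping rule should tell an investigator what to do with a given result. Here the section holding the list of stopping criteria and the section describing the event disagree on whether stopping is compulsory. The cross-reference between them leads to the weaker text and does not settle the matter.

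Hematologic abnormality is an event of special interest in this trial (8.5.6). The Protocol also names a possible increase in hematologic abnormality or marrow suppression as a risk of combining PegIFN-α2a with the investigational drugs (2.3.2.2.3).

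Three things are at stake: consistent handling of participants across sites, drug exposure, and the classification of deviations. SAP Appendix 4 has a major-deviation category for participants who met a withdrawal criterion and were not withdrawn. Someone kept on treatment in line with 8.5.6.5 or Table 5 could be placed in it under 7.1.

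**Working it through.** No sample size or error rate is involved. The check sets the DAIDS grade ranges in Appendix 9 against the three instructions, value by value.

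Inputs (cells/mm³ unless stated):
- DAIDS row "Platelets, Decreased": grade 3 is 25,000 to <50,000; grade 4 is <25,000.
- DAIDS ANC: grade 2 is 600–799, grade 3 is 400–599, grade 4 is <400.
- DAIDS hemoglobin, grade 3: 7.0 to <9.0 g/dL (men), 6.5 to <8.5 g/dL (women).
- Table 5, PegIFN-α2a only: platelets <50,000 reduce, <25,000 stop; ANC <750 reduce, <500 stop until above 1,000.

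| Confirmed value | DAIDS grade | 7.1, general list | 8.5.6.5 | Table 5 (PegIFN-α2a) |
|---|---|---|---|---|
| Platelets <25,000 | 4 | must stop | consider stopping | stop |
| Platelets 25,000 to <50,000 | 3 | must stop | consider stopping | reduce |
| ANC <400 | 4 | must stop | consider stopping | stop, restart allowed |
| ANC 400–499 | 3 | must stop | consider stopping | stop, restart allowed |
| ANC 500–599 | 3 | must stop | consider stopping | reduce |
| ANC 600–749 | 2 | not triggered | extra monitoring | reduce |
| Hemoglobin, grade 3 | 3 | must stop | consider stopping | no row |

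Overlap of grade 3 with the Table 5 reduction band:
- Platelets: 25,000 to <50,000 against 25,000 to <50,000, so the whole grade 3 range.
- ANC: 400–599 against 500–749, so 500–599.

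Reading by drug:
- JNJ-3989: two instructions at every confirmed grade 3 or 4 value. Table 5 cannot apply, because the dose may not be modified.
- PegIFN-α2a: the same two at every such value, and a third (reduce) in the two overlap ranges.

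The drugs are also linked. Under 7.1, stopping JNJ-3989 means PegIFN-α2a should stop too, while stopping PegIFN-α2a leaves JNJ-3989 running. During overlap, the section a site follows for JNJ-3989 therefore also decides what happens to PegIFN-α2a.

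Other criteria in 7.1 show that the hematologic mismatch is not simply house style. Rash of grade 3 or higher is a compulsory stop for JNJ-3989 in both 7.1 and Table 6. A persistent, related renal abnormality is compulsory in both 7.1 and 8.5.6.4. Where 7.1 wants discretion, as for virologic breakthrough during combined JNJ-3989 and PegIFN-α2a, it says so within the criterion. The hematologic criterion has no such text.

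**The case against.** The strongest defence is that a criterion which refers to another section defers to it. The ALT/AST criterion in 7.1 works this way: it sets no threshold of its own and points to 8.5.6.2, where an isolated elevation may be compatible with continuing. That reading is possible, but it does not fully rescue the hematologic criterion, which states its own threshold under a compulsory opening sentence.

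Several limits on the conflict with Table 5 do stand:
- The table is an example of labelling, applied on the investigator's assessment, and PegIFN-α2a is optional with separate consent.
- It asks for no confirmation, whereas 7.1 and 8.5.6.5 do. A site could reduce on the first value and turn to the other sections after the confirmatory visit. The three-way conflict therefore exists only once the value is confirmed.
- PegIFN-α2a starts after the Week 40 biopsy, so the Table 5 question cannot affect the primary endpoint.
- The last JNJ-3989 injection is at Week 44, so most of a 12- or 24-week PegIFN-α2a course falls later. The and/or wording in 7.1 may then allow another reading.

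A reader might also infer that the second list in 7.1 stops PegIFN-α2a only below 25,000 platelets and so contradicts the general list. The text does not say that. The second list is presented as additional and as requiring immediate action, so an immediate stop at the lower limit can coexist with a stop at confirmed grade 3.

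**Conclusion.** The contradiction between 7.1 and 8.5.6.5 is in the text and needs correction. It covers every confirmed grade 3 or 4 hematologic value for both drugs and stands without Table 5. The third instruction is confined to PegIFN-α2a, at confirmed platelets of 25,000 to <50,000 and confirmed ANC of 500–599.

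Two stronger readings are tempting and are not supported:
- A reader might infer that any such laboratory value draws three instructions. That fails for JNJ-3989, for hemoglobin, and for PegIFN-α2a outside the two ranges.
- A reader might infer that affected participants drop out of the per-protocol set. Under the category for unheeded withdrawal criteria, SAP Attachment 2 names only hepatic decompensation and virologic breakthrough. The demonstrated exposure is to the general coding category in Appendix 4, not to automatic exclusion.

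The number of participants affected cannot be derived from the documents. Section 2.2.2.1 reports hematologic events or abnormalities in around 5% of a related Phase 2 study, mostly mild to moderate, so confirmed grade 3 values may be few. That figure does not describe participants given PegIFN-α2a.

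The conclusion assumes DAIDS grading throughout, as 7.1 states, and the Table 5 limits as printed; local labelling could shift the overlap ranges.

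**What to change.** The sponsor should reconcile Sections 7.1, 8.5.6.5 and 6.6 with Table 5. The reconciled text should state which section governs JNJ-3989 and which governs PegIFN-α2a, and how Table 5 relates to the confirmatory visit. Asking for one instruction per DAIDS grade would go too far: grade 3 ANC (400–599) straddles the Table 5 limit of 500. The choice of rule is a clinical decision for the sponsor.

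Deviation coding under SAP Appendix 4, and Attachment 2 if relevant, should then follow the reconciled text. For participants already treated, the coding should be settled before database lock.

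The cost is protocol clarification or amendment wording and a small change to the deviation rules. No visits, samples or analyses are added.

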### **8.5.7. Other Toxicities**

#### **8.5.7.1. Rash**

Participants should be informed that they should contact their doctor immediately when they notice any generalized skin reaction. This skin reaction should be evaluated in the clinic the same day (if possible) or the next day.

All rash events should be captured in the special events section of the CRF. A set of separate Rash pages will be completed in case of a rash event.

Monitoring of the evolution of rash events will be performed as described in [Table 6](#) in Section [10.5](#), Appendix 5, Rash Management.

When safety blood samples are drawn as per the rash management guidelines, these should be processed by the local laboratory. The following parameters will need to be tested: AST, ALT, sedimentation rate, complete blood cell count (including hemoglobin, hematocrit, RBC count, WBC count, differential count [neutrophils, lymphocytes, monocytes, eosinophils, and basophils], and platelet count), and creatinine. The values of the local laboratory assessments need to be transcribed in the CRF by the study site personnel.

The participant may be treated symptomatically until the rash resolves. Oral antihistamines (eg, cetirizine, levocetirizine) and/or topical corticosteroids may provide symptomatic relief but effectiveness of these measures has not been established. If systemic corticosteroids exceeding 5 mg of prednisolone equivalent/day are required for treatment of rash, JNJ-3989 (and PegIFN- $\alpha$ 2a, if applicable) needs to be permanently discontinued. NA treatment can be continued. If the rash is considered to be most likely due to concomitant illness or non-study interventions, standard management, including discontinuation of the likely causative agent, should be undertaken.

#### **8.5.7.2. Acute Systemic Allergic Reactions**

##### **Grade 1 (Localized Urticaria [Wheals] With no Medical Intervention Indicated)**

Participants may continue the intake of study interventions.

Cetirizine, levocetirizine, topical corticosteroids or antipruritic agents may be prescribed.

Participants should be advised to contact the investigator immediately if there is any worsening of the acute systemic allergic reaction.

##### **Grade 2 (Localized Urticaria With Intervention Indicated, or Mild Angioedema With no Intervention Indicated)**

Participants may continue the intake of study interventions.

Cetirizine, levocetirizine, topical corticosteroids or antipruritic agents may be prescribed.

Participants should be advised to contact the investigator immediately if there is any worsening of the acute systemic allergic reaction, in which case the participant will permanently discontinue the intake of JNJ-3989 (and PegIFN- $\alpha$ 2a, if applicable). Rechallenge is not allowed. The participant's NA treatment may be discontinued based on investigator judgement in consultation with the sponsor.

**Grade 3 (Generalized Urticaria, Angioedema With Intervention Indicated, or Symptoms of Mild Bronchospasm) and Grade 4 (Acute Anaphylaxis, Life-Threatening Bronchospasm, or Laryngeal Edema)**

Participants will permanently discontinue the intake of JNJ-3989 (and PegIFN- $\alpha$ 2a, if applicable). Rechallenge is not allowed. The participant's NA treatment may be discontinued based on investigator judgement in consultation with the sponsor.

Participants will be treated as clinically appropriate. Participants should be followed until resolution of the AE and standard management should be undertaken.

**8.6. Treatment of Overdose**

For this study, any dose of JNJ-3989 greater than the protocol-specified dose (refer to Section 6.1) will be considered an overdose; any dose of NA (ETV, tenofovir disoproxil, or TAF) and PegIFN- $\alpha$ 2a greater than the prescribed dose will be considered an overdose. The sponsor does not recommend specific therapeutic intervention for an overdose.

In the event of an overdose, the investigator or treating physician should:

- Contact the Medical Monitor immediately.
- Closely monitor the participant for AE/SAE and laboratory abnormalities.
- Obtain a plasma sample for PK analysis as soon as possible from the date of the last dose of study intervention if requested by the Medical Monitor (determined on a case-by-case basis).
- Document the quantity of the excess dose as well as the duration of the overdosing in the CRF.

Decisions regarding dose interruptions or modifications will be made by the investigator in consultation with the Medical Monitor based on the clinical evaluation of the participant.

